**SYNOPSIS**

Title: A Multicenter, Open-Label Trial to Evaluate the Overall Performance of the Zalviso System (sufentanil sublingual tablet system) 15 mcg	
Sponsor: AcelRx Pharmaceuticals, Inc. Investigational Product: sufentanil sublingual tablet system, 15 mcg Active Ingredient: sufentanil citrate	
Investigators: Multicenter Country: USA	Protocol No.: IAP312 Clinical Phase: 3
Patients: Up to 330 adult postoperative in-patients who are expected to require opioid analgesia for at least 24 hours, and up to 72 hours, after surgery will be enrolled in order to ensure at least 315 patients will receive study drug and provide Zalviso (sufentanil sublingual tablet system) 15 mcg performance data for analysis.	

Study Objectives: The objectives of this study are:
 
 
• Assess device dispense failure rate with the modified Zalviso System design
 
• Assess impact of System error 302 mitigations on overall System usability
 
• Assess the incidence of misplaced tablets and drug accountability while patients were using the Zalviso System
 
• Evaluate patient and nurse usability of, and satisfaction with, the Zalviso System to treat moderate-to-severe postoperative pain
 
• Evaluate the efficacy and safety of the Zalviso System to treat moderate-to-severe postoperative pain
 
	

Trial Design: The study is a multicenter, open-label trial for 24 hours, and up to 72 hours, in patients 18 years and older who are undergoing surgery and are expected to require opioid analgesia for at least 24 hours. Patients who meet all inclusion and exclusion criteria at screening and following surgery will receive the Zalviso System.
 
Non-opioid analgesics may be used at any time along with the Zalviso System in a multimodal approach to the treatment of the patient’s postoperative pain. However, supplemental opioid medication (2 mg IV morphine) will only be allowed in the first 30 minutes after the first on-demand dose of study drug has been administered if necessary to keep a patient comfortable. Otherwise, supplemental opioid medication (2 mg IV morphine, no more frequently than hourly) is allowed only for pain due to ambulation or with the initiation of passive range of motion therapy throughout the remainder of the study. A pain intensity and pain relief score should be obtained prior to each administration of supplemental opioid medication.
 
Overall device performance and usability of the Zalviso System will be assessed by: proportion of patients with system-generated (device) errors and other failures of the device to function properly, number of patients with misplaced tablets (tablets inadvertently dispensed or dosed outside of the mouth), as well as the number of misplaced tablets, as assessed by study staff checks every 2 hours, and the Patient Usability Questionnaire (PUQ). Usability will also be assessed using the Nurse Usability Questionnaire (NUQ) which will be completed by study staff after they have experience with 5 or more patients or at the end of the study at the site.
	

Pain intensity will be self-recorded by the patient prior to first dose of study drug and then pain relief and pain intensity will be recorded by the patient at the following time points after the first on-demand dose of study drug:  $\frac{1}{4}$  [15 min],  $\frac{1}{2}$  [30 min],  $\frac{3}{4}$  [45 min], 1, 2, 4, 6, 8, 10, and 12 hours, then every 4 hours at 16, 20, 24, 28, 32, 36, 40, 44, 48, 52, 56, 60, 64, 68, and 72 hours. **During the study period, all PI, PR, and the patient global assessment (PGA) scores will be self-recorded by the patient in a source document provided by investigator's staff per the study schema.** The study staff must not record the patient's PI, PR, or global scores for the patient.

Satisfaction with analgesia will be assessed by: patient global assessment (PGA) and healthcare professional global assessment (HPGA) of the method of pain control on a four point scale where 1 = poor, 2 = fair, 3 = good, and 4 = excellent, patient reports of pain intensity on an 11-point numerical rating scale (NRS), where 0 = no pain, and 10 = worst possible pain, a five-point pain relief scale (0 = no relief, 1 = a little relief, 2 = moderate relief, 3 = a lot of relief, 4 = complete relief), and percentage of patients dropping out of the study due to inadequate analgesia. Also, the total number of doses of study drug administered will be recorded and average hourly use will be calculated from the dosing information. Use of supplemental opioid medication will also be recorded.

Patients displaying any one of the following:

- oxygen saturation levels that cannot be maintained at 95% or greater with or without the use of supplemental oxygen
- respiratory rate less than 8 bpm
- excessive sedation

will not be allowed to have access to study drug or supplemental opioid medication until these vital signs have improved. **Sites must document improvement of these vital signs in the source and eCRF.**

If the oxygen saturation is below 95% with supplemental oxygen, even if no other vital sign is abnormal and the patient does not improve following 2 arousal and vital sign checks 3 minutes apart, then the patient should be removed from the study.

If the respiratory rate is low (below 8 bpm but oxygen saturation is greater than or equal to 95% and no excessive sedation is present) or if excessive sedation exists (respiration and oxygenation are above limits), and each adverse event does not improve within 20 minutes under supervision with every 3 minute arousal and vital sign checks after discontinuing access to study drug, the patient should be removed from the study. If these two adverse events (low respiratory rate and excessive sedation) should occur simultaneously, then the more conservative withdrawal criteria should be followed: the patient should be removed from the study if after two arousal and vital sign checks 3 minutes apart, these symptoms do not improve.

**All vital signs measured to manage oxygen desaturation and decreased respiratory rate must be recorded in the source and eCRF.**

Heart rate and blood pressure will be recorded prior to administration of the first dose of study drug, and then when pain intensity and pain relief assessments are recorded at the following time points after the first on-demand dose: ¼ [15 min], ½ [30 min], ¾ [45 min], 1, 2, 4, 6, 8, 10, and 12 hours, then every 4 hours at 16, 20, 24, 28, 32, 36, 40, 44, 48, 52, 56, 60, 64, 68, and 72 hours. These assessments may be collected up to 5 minutes before scheduled time to allow for the PI and PR assessments to be made at the scheduled time.

During the first 24 hours after the first dose of study drug, respiratory rate and oxygen saturation will be recorded prior to the first dose of study drug, then 15, 30, 45, and 60 minutes after the first dose of study drug, and then every 30 minutes. After 24 hours, respiratory rate and oxygen saturation will be recorded every 2 hours. These assessments may be collected up to 5 minutes before scheduled time to allow for the PI and PR assessments to be made at the scheduled time.

Safety will be monitored via periodic measurement of vital signs, continuous monitoring of oxygen saturation, assessment of adverse events (AEs), and the use of concomitant medications.

**Inclusion Criteria at Screening:**

1. Male or female patients who are 18 years of age or older.
2. Patients who are scheduled to undergo surgery under general or spinal anesthesia that does not include intrathecal opioids during the operation.
3. Patients classified as American Society of Anesthesiologists (ASA) class I - III (Appendix I).
4. Female patients of childbearing potential must be using an effective method of birth control at the time of screening visit and for 30 days following the end of the study period. Acceptable methods of birth control include oral or transdermal contraceptives, condom, spermicidal foam, intrauterine device (IUD), progestin implant or injection, abstinence, vaginal ring, or sterilization of partner. The reason for non-child bearing potential, such as bilateral tubal ligation, bilateral oophorectomy, hysterectomy, or postmenopausal for > 1 year, must be specified. Patients using hormonal forms of contraception must also be willing to use a barrier method of contraception from screening through 30 days following the study period.
5. Post-surgical patients who have been admitted to the PACU, and are expected to have acute pain requiring opioids for 24 – 72 hours after surgery.
6. Patients who have the manual dexterity to handle the Zalviso System and are able to follow directions for use.
7. Patients who are willing and capable of understanding and cooperating with the requirements of the study.
8. Patients able to understand and communicate in English.
9. Patients who have provided written informed consent and signed the IRB approved consent form.

Exclusion Criteria at Screening

1. Patients who have taken an opioid for more than 30 consecutive days, at a daily dose of 15 mg or more of morphine (or equivalent), within the past 3 months prior to surgery (e.g. more than 3 doses per day of Vicodin®, Norco®, Lortab® with 5 mg hydrocodone per tablet).
2. Patients with a positive drug of abuse urine screen unless the positive test result is consistent with a prescribed medication
3. Patients with a history of opioid dependence within two years before the start of the study, defined as meeting the DSM-IV-TR™ Criteria for Substance Dependence specified in Appendix II.
4. Patients who have used any illicit drugs of abuse within five years before the start of the study.
5. Patients who have abused any prescription medication or alcohol within one year before the start of the study.
6. Patients with an allergy or hypersensitivity to opioids.
7. Patients who are currently taking monoamine oxidase inhibitors (MAOIs) or have taken MAOIs within 14 days of the first dose of study drug.
8. Patients with current sleep apnea that has been documented by a sleep laboratory study or are on home continuous positive airway pressure (CPAP).
9. Female patients who are pregnant (positive pregnancy test at screening or after hospital admission), breastfeeding or planning to breastfeed within 30 days of the last dose of the study drug.
10. Patients with a medical condition that, in the Investigator's opinion, could adversely impact the patient's participation or safety, conduct of the study, or interfere with the pain assessments, including chronic pain or active infection.
11. Patients who have cancer and are receiving radiation/chemotherapy and are expecting to receive radiation/chemotherapy within 72 hours after surgery.
12. Patients who require an additional scheduled surgical procedure within 72 hours of the surgery.
13. Patients who are expected to have postoperative analgesia supplied by a long-acting or continuous regional technique (e.g., spinal opioids or continuous nerve block).
14. Patients who received surgical premedication with long-acting opioid analgesics.
15. Patients who are receiving oxygen therapy at the time of screening.
16. Patients who have participated in a clinical trial of an investigational drug or device within 30 days of screening visit or is scheduled to receive an investigational product while participating in this study.

Exclusion Criteria Post-Surgery:

1. Patients who are not awake, not breathing spontaneously or have a respiratory rate that is less than 8 breaths per minute or greater than 24 breaths per minute.
2. Patients with arterial oxygen saturation by pulse oximetry (SpO2) that cannot be maintained at 95% or greater with or without supplemental oxygen.
3. Patients not able to answer questions and follow commands.
4. Patients who are vomiting and not responsive to standard treatment.

5. Patients who have any deviation from the surgical or anesthetic protocols as specified in Section 6.1.2.1 of the protocol


Efficacy Variables and Parameters are:
 
 
• Proportion of patients who experienced at least one system-generated error based on the Controller data while using the Zalviso System
 
• Proportion of patients, if any, with tablet dispensed but not requested
 
• Proportion of patients, if any, with tablet dispensed when the Zalviso System is in lockout
 
• Proportion of patients with misplaced tablet(s)
 
• Number of misplaced tablets (i.e., tablet found outside the patient’s mouth)
 
• Proportion of patients who experienced either a system-generated error or a misplaced tablet (i.e. a dispense failure)
 
• Assessment of the number of Zalviso System notifications to the nurse to retrain patient to not pull down on Controller while dosing (i.e., mitigation of Error 302)
 
• Proportion of patients who rate the Patient Global Assessment (PGA) of method of pain control over 24, 48 and 72 hours as “good” or “excellent”
 
• Proportion of patients who responded in each category of the PGA
 
• Proportion of Healthcare Professionals who rate the Global Assessment (HPGA) of method of pain control over 24, 48 and 72 hours as “good” or “excellent”
 
• Proportion of Healthcare Professionals who responded in each category of the HPGA
 
• Proportion of patients who terminate from the study due to inadequate analgesia over the 24-hour, 48-hour and 72-hour study period
 
• Time-weighted summed pain intensity difference (SPID) over the 24-hour study period (SPID24), over the 48-hour study period (SPID48), and over the 72-hour study period (SPID72)
 
• Total pain relief (TOTPAR) over the 24-hour study period (TOTPAR24), over the 48-hour study period (TOTPAR48) and over the 72-hour study period (TOTPAR72)
 
• Pain intensity (PI) at each evaluation time point
 
• Pain intensity difference (PID) at each evaluation time point
 
• Pain relief (PR) at each evaluation time point
 
• Patient Usability Questionnaire (PUQ)
 
• Nurse Usability Questionnaire (NUQ)
 
• Total number of study drug doses used over 24, 48, and 72-hour study period, average hourly use, and average inter-dosing interval.
 
• Total amount of supplemental morphine utilized
 


Safety Variables: Safety assessments will include the assessment of adverse events, vital signs (blood pressure, heart rate, and respiratory rate), oxygen saturation, and the use of concomitant medications.

Determination of Sample Size: This is a multicenter, open-label, single treatment clinical study designed to evaluate the overall functionality of the Zalviso System (sufentanil sublingual tablet system) 15 mcg for the treatment of acute moderate-to-

severe postoperative pain. A sample size of approximately 330 patients is planned for this study in order to have at least 315 patients receive study drug and have available efficacy data for data analysis.

A sample size of 315 patients will have 90% power to demonstrate that the device dispense failure rate is non-inferior to a target of 2%. This failure rate is the proportion of patients who experienced at least one of following events: (1) a system-generated error, (2) a tablet dispensed but not requested, or (3) a tablet dispensed when the Zalviso System is in lockout. All events listed above will be obtained from the Controller patient usage data.

This is based on the criteria that the upper limit of a 90% confidence interval (CI) of the device dispense failure rate is not worse than 5%. This calculation is based on the exact binomial test of one-sample proportion for a one-sided case against a 2% target proportion with a delta of 3%, and a one-sided significance level of  $\alpha=0.05$ . This sample size was generated from the SAS procedure PROC POWER for one-sample proportion. Exact power computations are based on the binomial distribution and computing formulas provided by Johnson and Kotz (1970). Assuming a 5% non-evaluable rate, a sample size of 330 patients is planned for this study.

**Statistical Analysis:** The main analysis of the efficacy variables will include the intent-to-treat (ITT) population. The ITT population includes enrolled patients who received study drug. Demographics and baseline characteristics will be summarized by sex group for all enrolled patients and ITT population. Data will be pooled for all study centers for the descriptive summary of baseline data. No formal hypothesis testing will be performed for baseline data.

The data from all study centers will be pooled for the analysis of efficacy data. Both continuous and categorical efficacy variables will be summarized descriptively. A point estimate of the device dispense failure rate and its 90% confidence interval based on the exact binomial test will be constructed. For the analysis of the dichotomous outcome data, a point estimate and its 90% confidence interval based on the exact binomial test will be constructed.

All patients who received at least one dose of study drug will be included in the summaries of safety data. An AE thesaurus, the Medical Dictionary for Regulatory Activities (MedDRA) will be used to map each AE verbatim term to lowest level term, preferred term, and System Organ Class for summary purposes. Adverse events occurring while patients are on study drug until 12 hours after the last dose will be summarized. Other safety data, such as premature terminations, vital signs (blood pressure, heart rate, and respiratory rate), oxygen saturation, and the use of concomitant medications will be tabulated.

Vital signs taken at baseline and follow-up time points will be summarized. Patients who had baseline data and at least one follow-up data will be included in the summary of vital signs by sex group. The descriptive summary statistics will be presented. A

paired t-test will be used for the test of mean change from baseline to follow-up time points within each group.

**Study Schema – Screening**

Procedures	Screening (within 30 days of surgery)
Patient Informed Consent	✓
Inclusion and Exclusion Criteria	✓
Medical History	✓
Vital Signs	✓
Physical Exam	✓
Urine Drug Abuse Screen	✓
Urine Pregnancy Test	✓

**Study Schema– Randomization and Study Treatment**

Procedures	Hospital Admission	Post-Surgery	0 - 24 hr Treatment Period	24 - 48 hr Treatment Period	48 – 72 hr Treatment Period	Study Completion or Early Termination
Urine pregnancy test	✓					
Confirm Patient Continue to Meet Entrance Criteria		✓				
Baseline Pain Intensity (just prior to 1 st dose)			✓			
Dosing (record date/time 1 st and last dose)			✓			✓
Continued Zalviso Dosing			✓	✓	✓	
Blood Pressure and Heart Rate			✓ A	✓ B	✓ B	
Respiratory Rate and Oxygen Saturation			✓ C	✓ D	✓ D	
Pain Intensity and Pain Relief Assessments			✓ A	✓ B	✓ B	✓
Record Number of Doses from Controller			✓ A	✓ B	✓ B	
Check for Misplaced Tablets			✓ E	✓ E	✓ E	
Patient and Healthcare Professional Global Assessments			✓ F	✓ F	✓ F	✓
Patient and Nurse Usability Questionnaire						✓ G
System-Generated Errors			✓	✓	✓	
Study Drug Accountability						✓
Record Concomitant Meds	✓	✓	✓	✓	✓	✓
Record AEs			✓	✓	✓	✓

A Record prior to first dose and at ¼ [15 min], ½ [30 min], ¾ [45 min], 1, 2, 4, 6, 8, 10, and 12 hours after 1st on-demand dose, then every 4 hours at 16, 20, and 24 hours after 1st on-demand dose.

BRecord every 4 hours at 28, 32, 36, 40, 44, 48, 52, 56, 60, 64, 68, and 72 hours after the 1st on-demand dose.

CRecord prior to first dose and at 15, 30, 45, 60 minutes after 1st on-demand dose and then every 30 minutes after 1st on-demand dose through 24 hours.

D Record every 2 hours at 26, 28, 30, 32, 34, 36, 38, 40, 42, 44, 46, 48, 50, 52, 54, 56, 58, 60, 62, 64, 66, 68, 70, and 72 hours after the 1st on-demand dose.

ECheck for and record any misplaced tablets every 2 hours after 1st on-demand dose.

F The PGA and HPGA will be completed at 24 hours, 48 hours and 72 hours. If the patient withdraws prior to 24 hours, the global assessments should be administered at the time of early termination.

G Each patient will complete an Usability Questionnaire at the end of his/her participation in the study and prior to completing the PGA; the study staff at each site will complete the Usability Questionnaire after he/she has completed 5 patients on the study or at the time the study is completed at the site.

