### **5.5 Drug Accountability**

The Investigator, dispensing pharmacist, and nursing staff will be responsible for maintaining the medication accountability log, which will contain inventory records acknowledging receipt of study drug, and dispensing records tracking distribution of medication to patients. All used and unused cartridges will be kept at the site until study completion. At study closeout, the Investigator will be required to reconcile all received, dispensed, used, and unused drug cartridges, and return to AcelRx, or its designee for destruction as per instructions from AcelRx. Unused Zalviso System supplies will be handled according to directions from AcelRx.

When a patient is discontinued or a replacement Drug Cartridge is needed, the number of tablets remaining in the used Drug Cartridge as displayed on the Zalviso System display screen will be recorded in the source records. Appropriate source records will be sent to AcelRx or designee along with the used and unused Drug Cartridges for tablet accountability. AcelRx or designee will count the number of tablets remaining in each used Drug Cartridge using the HP-IFU manual method and compared to the site's source records. Any discrepancies will be investigated.

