- If the patient cannot take a dose, the Zalviso System's blue and green lights are continuously flashing and the Zalviso System is beeping, call the study staff
- If the patient notices a misplaced tablet, call the study staff

The criteria for the study period to begin are:

- the patient has been discharged from the PACU (or is ready for discharge)
- the patient has reported a pain score of  $>4$  just prior to the first dose of study drug (baseline pain intensity)
- the patient has requested medication for pain

Patients should not eat or drink and should minimize talking for 10 minutes after a tablet has been self-administered. Ice chips may be used to avoid excessively dry mouths in patients during the study period. Additional doses will be self-administered by the patient as needed to maintain analgesia.

During the study period all pain intensity, pain relief, and global assessment scores will be self-recorded by the patient in a source document provided by investigator's staff per the study schema. The patient and study staff will complete a PGA and HPGA, respectively, 24 hours, 48 hours and 72 hours after the first dose of study drug. If the patient discontinues before 24 hours, the PGA and HPGA assessments will be completed by the patient and study staff at the time of early termination.

During the study treatment period, the study staff will check for any misplaced tablets every 2 hours starting with the 1st on-demand dose. This would include checking the Zalviso System cap, within the patient's bed and linens, and on the hospital room floor. If a misplaced tablet is found, the study staff will document in the source and eCRF including the details of when and where found, and query the patient to determine the likely cause of the misplaced tablet. The patient will be retrained on proper dosing technique.

The study staff will record the date and time of the first and last doses of study drug taken during the study period from the Controller's detailed history log.

Should a patient use all 40 tablets and require additional analgesia within the study period, an additional drug cartridge will be provided.

If a patient is asleep at the time of a protocol-specified pain rating or vital signs assessment, the patient will be allowed to sleep, but the study staff will record the respiratory rate and oxygen saturation. A patient will not be allowed to sleep through 2 consecutive assessments.

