#### **6.1.4 End of Study**

Patients will be considered completers if they complete the study for a minimum of 24 hours. Patients who are withdrawn from the study for any reason prior to 24 hours will be considered early terminations.

At the time the patient discontinues from the study or a Drug Cartridge is changed, the number of tablets remaining in the Drug Cartridge as displayed on the Zalviso System display screen will be recorded in the source records.

The Patient Usability Questionnaire (Appendix IV) will be completed at the end of the study or at the time of early discontinuation. The Patient Usability Questionnaire will be completed before the patient completes the PGA (Appendix III).

Study staff will complete the Nurse Usability Questionnaire (Appendix V) when they have interacted with 5 patients, or when enrollment is completed at the study site. The study staff will download the controller data after its use by each patient using the data transfer cable and download utility software provided by AcelRx. The data files will then be transferred per AcelRx instructions.

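### No misplaced-tablet search is scheduled when the System is stopped, so a tablet dropped after the last 2-hourly check can go uncounted when a patient stops between checks

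*Protocol*

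**What the plan says.** The incidence of misplaced tablets is a stated objective (Protocol section 2). It supplies efficacy variables 4 (proportion of patients), 5 (number of tablets) and 6 (patients with a system-generated error or a misplaced tablet), with the same numbering in Protocol 9.5.1 and SAP 2.10.1.

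Active ascertainment is described in three places, all tied to a 2-hour cycle:

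- The Synopsis describes the number of patients and tablets "as assessed by study staff checks every 2 hours".
- In the treatment schema, the row "Check for Misplaced Tablets" is ticked for the three treatment periods and blank for completion or early termination. Footnote E reads "Check for and record any misplaced tablets every 2 hours after 1 st on-demand dose".
- Section 6.1.3 says "During the study treatment period, the study staff will check for any misplaced tablets every 2 hours starting with the 1 st on-demand dose", and names the cap, the bed and linens, and the floor.

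At the end of participation, section 6.1.4 requires that "the number of tablets remaining in the Drug Cartridge as displayed on the Zalviso System display screen will be recorded in the source records", along with the questionnaires and the Controller download. It mentions no search. Section 5.4 stops both System and patient after a system error or suspected technical failure, again without a search. Section 5.5 adds a later reconciliation, in which the sponsor or its designee "will count the number of tablets remaining in each used Drug Cartridge" and compares the result with the site's records.

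There is also passive capture. Section 5.4 requires any misplaced tablet found by patient or staff to be documented, and section 6.1.3 has patients trained to call staff if they notice one.

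**The concern.** A 2-hourly search covers the time up to the most recent check. When the System is removed between checks, nothing in the plan triggers a search of the remaining part-interval. Stops for a system error, suspected technical failure, adverse event or inadequate analgesia have no reason to fall on an even hour, so the gap lies mainly in early terminations.

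The direction is known: an unsearched interval can only lower the count, which favours the System. The timing may not be neutral either. The protocol links Error 302 to pulling down on the Controller while dosing, so such an error can end participation around a dosing attempt, when a tablet could also be misplaced. At stake are complete ascertainment of a named objective and the physical recovery of a Schedule II tablet.

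**Working it through.** **The plan's own figure.** Section 9.1 states 90% power with 315 patients for a true rate of 2% against a 5% limit, at one-sided alpha 0.05. The largest c with P(X ≤ c | 315, 0.05) ≤ 0.05 is c = 9, with exact alpha 0.0449. Power is P(X ≤ 9 | 315, 0.02) = 0.896, so the figure reproduces. The events in that rate are system-generated errors, tablets dispensed but not requested, and tablets dispensed in lockout, all from Controller data. Misplaced tablets are not among them, so neither the gap nor its repair changes this calculation.

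**Is the gap closed elsewhere?**

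- *Schema.* The completion/early-termination column is blank for this row but ticked for pain assessments, global assessments, drug accountability, concomitant medications and AEs.
- *Section 4.4.* Data normally collected at completion must also be collected at early termination. The search is not a completion procedure, so this rule does not bring it in.
- *Section 5.5.* Tablets left in the cartridge are compared with the site's record of the display. A tablet dispensed and then dropped has left the cartridge on both counts, so no discrepancy appears. Section 5.1.2 says the electronics detect singulation; it does not describe detecting arrival in the mouth.

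**Length of the unsearched tail.** With checks at 2, 4, 6 h and so on, a stop at T hours leaves T − 2 × floor(T/2) hours unsearched:

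- T = 24, 48 or 72 h: 0 h, as for any stop on an even hour.
- T = 3 h: 3 − 2 = 1 h, or 1/3 = 33% of exposure.
- T = 25 h: 25 − 24 = 1 h, or 1/25 = 4.0% of exposure.
- T below 2 h: possibly no scheduled search after dosing.

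The range is 0 to 2 h. If stops are uniform within the cycle (an assumption), the mean is (0 + 2)/2 = 1 h.

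**Tablets dispensed in the tail.** Section 1.1 describes 40 tablets as about a 2-day supply: 40/48 = 0.83 per hour.

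- Mean tail: 1 × 0.83 ≈ 0.8 tablets.
- Full 2 h: 2 × 0.83 ≈ 1.7 tablets.
- Ceiling under the 20-minute lockout: 120/20 = about 6 tablets.

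These are tablets dispensed, not tablets lost.

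**Effect on the endpoints.** The expected number missed would be (off-schedule stops) × (tablets in the tail) × (misplacement probability per tablet) × (probability of not being noticed). The documents give no value for the first, third or fourth factor, so no estimate is possible. The effect per patient is known: each one missed lowers a patient-level proportion by 1/315 = 0.32 percentage points.

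**Which items can change.** Items 4 and 5 can change for any off-schedule stop. Item 6 can change only for a patient without a system-generated error, because a patient with one already counts.

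**The case against.** The strongest reply is that tablets are not simply lost to the record. Patients are trained to report them, and anything found by patient or staff at any time must be documented. Early exposure is also closely watched: the first dose is observed, the first hour is continuously monitored (section 6.1.3), and respiratory rate and oxygen saturation are recorded every 30 minutes to 24 h. This stands, and it limits the claim to tablets that *can* be missed. It does not close the gap, because noticing a tablet is not the same as the active search of cap, bed, linens and floor that the protocol asks for every 2 hours.

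The blank schema cell alone is weak evidence. The row for system-generated errors is blank in the same column, although such an error itself ends participation. The firmer support is that sections 5.4, 6.1.3 and 6.1.4 are all silent on a search at the stop.

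Section 5.4 also refers to the HP-IFU, which is not among the documents and might contain a take-down search. Even so, the protocol and SAP do not require the result of such a search to be recorded for the endpoint.

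A reader might infer three stronger things that the documents do not support:

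- *That a patient stopped before 2 h goes unobserved.* Such a patient may have no scheduled search, but the monitoring above applies.
- *That the 5% success criterion is at risk*, because item 6 also carries the label of a dispense failure. Section 9.1 defines the sized rate from Controller events alone.
- *That a loose tablet is left in a room the patient vacates.* The documents do not say that. Patients stopped for device failure or uncontrolled pain go on to alternate postoperative analgesia at the site.

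**Conclusion.** The point holds as a narrow gap in ascertainment. Followed exactly, the plan can under-count misplaced tablets after stops that do not coincide with a 2-hourly check, and any such error favours the System. The tail averages 1 h only under the assumption of uniform stop times, and the 0.8-tablet figure also relies on the protocol's approximate usage. The total effect on items 4 and 5, and on the eligible part of item 6, is unknown and may be small. The primary sizing and power stand. The change is worth making because it completes a named objective at almost no cost, not because the main conclusion is in doubt.

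**What to change.** - In the treatment schema, tick the row "Check for Misplaced Tablets" under completion or early termination.
- In section 6.1.4, cross-referenced from 5.4, state that the cap, bed, linens and floor are checked, and the result recorded even if nothing is found, whenever the System is removed for any reason. Name system error and suspected technical failure explicitly.
- In SAP 2.10.1, state that a tablet found at this final check counts in items 4, 5 and 6.
- Confirm whether the HP-IFU already has a take-down search and, if so, align the wording.

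The cost is a few minutes per patient for staff already taking down the System, plus one tick and a few sentences. The observed misplaced-tablet rate may rise slightly. The sample size does not change.
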